Infections continue to be a considerable cause of death and disease among infants in low-and middle-income countries. In sub-Saharan Africa, infections contribute to 3/4 of under-five mortality. In previous studies of children in Tanzania, we observed that blood-stream infections (BSIs) caused by Gram-negative bacteria (*Enterobacteriales*) with extended-spectrum beta-lactamase (ESBL)-type resistance gave a mortality rate of more than 70%, compared to 20% or less for malaria infections or BSI with susceptible bacteria. An increasing prevalence of ESBL-producing *Enterobacteriales* (ESBL-E) are among the most urgent global health threats, and ESBL-E are by WHO ranked on priority 1 among pathogens in need of new treatment. We have previously shown in a study from Tanzania that around 2/3 of infants below three months of age had faecal carriage of ESBL-E.

Probiotics are live microorganisms that, when administered in adequate amounts, confer a benefit to the host. Probiotics are currently widely used in newborns and children. They have proven beneficial effects in preterm infants with reductions in the incidence of necrotizing enterocolitis (NEC) and sepsis. For this patient group the use of probiotics in high-income countries has entered what has been called a “golden age”, and similar beneficial effects have also been observed among preterm infants in low- and middle-income countries. Probiotics may also reduce colonization by ESBL-E and other antibiotic resistant bacteria through “colonization resistance”, but there is limited data on which probiotic strains that most effectively reduce ESBL-E carriage in children. In adults and older children lactobacilli are often used to prevent or treat other conditions like antibiotic-associated diarrhea, gastroenteritis and infantile colic. A recent large clinical trial from India reported reduced mortality and fewer severe infections in children receiving probiotics combined with a fructo-

ProRIDE Trial in Tanzania

oligosaccharides (prebiotic).

The present clinical trial will evaluate whether use of probiotics can reduce infection-related morbidity and mortality by preventing colonization and/or infections with ESBL-E among infants in Haydom, Tanzania.

Methods and expected results:

This is a single center randomized double-blind controlled clinical trial (RCT) with two arms, one intervention group (n=1000) randomized to receive a triple-strain probiotic product (Investigational product-IP) and one group (n=1000) randomized to receive placebo. The study will be conducted at Haydom Lutheran Hospital (HLH), in the northern-central part of Tanzania. A total of 2000 newborn infants will be enrolled in the study from day 0 - 3 after birth and they will be followed-up for a period of six months. We are planning to have three follow-up visits after enrollment between day 0-3. The first visit will be after 7 (6-9) days, the second at six weeks (35-50 days) and the third at six months (170-190 days) after study enrollment. Three electronic case report form (CRF) using RED cap, one for each visit, will be used to collect clinical and demographic information of the infants enrolled in the study. The initial data at enrollment will also be filled with mother's demographic and clinical information.

The IP and the placebo will be administered to the infant daily by the caretaker, from the day of enrollment and for a period of four weeks or more. One fecal swab and one fecal sample will be collected at the second and third visit, respectively, and analyzed for i) carriage of ESBL-E; ii) gut microbiota/metabolome composition incl. antibiotic resistome and iii) gut inflammation markers.

During the study period, we will also in a separate study investigate all causes of fever among children below 6 months admitted to the pediatric ward at HLH, including both study participants and children not included in the RCT. For this sub-study a separate inclusion form will be used. All children below 6 months admitted to HLH with fever during the study

ProRIDE Trial in Tanzania

period, will be offered blood culture diagnostics, including species identification and antibiotic susceptibility testing of pathogens in positive cultures, C-reactive protein (CRP) test, and malaria rapid test, the latter only if clinically indicated. An additional fecal swab sample will be obtained on acute admissions. Results will be communicated back to the attending clinician to assist management of these children. At a later stage, the stored fecal swab samples will be screened for ESBL-E using selective media (e.g. ESBL ChromID, BioMerieux). ESBL-E isolates from the fecal swab samples and from blood cultures obtained from children with fever will be further characterized using whole genome sequencing to detect ESBL-encoding genes and other genes encoding antibiotic resistance, and for molecular epidemiology purposes. Microbiota analysis will be performed on stored fecal samples using a metagenomics approach. Bioinformatic analysis will be performed using available and relevant software and methods. Statistical analysis of the study results will be performed using Stata 13 software.

This study is expected to show reduction in ESBL-E carriage in infants receiving probiotics. It is also powered to detect a 50% reduction in infection related morbidity and mortality among the group of infants treated with probiotics.

Budget and source of funding: The budget for conducting the RCT will be 184.000 USD. This RCT received funding from the Regional Health Trust of Western Norway.

1. Introduction

1.1 Background Information

Infections continue to be a considerable cause of death and disease among infants in low-and middle-income countries. In sub-Saharan Africa, infections contribute to 3/4 of under-five mortality (Kipp 2016). Although child mortality is declining in Sub-Saharan Africa, it is still very high. In Tanzania, the under-five mortality was reported at 55 per 1000 live births in 2016, whereof 42 deaths occurred before the age of one year (Wang 2017). Newborns are susceptible to infection because key parts of their immune systems are still developing and not fully functional (Goenka 2015 & Shane 2017). From our previous studies of hospitalized children in Tanzania, we have shown that blood-stream infections (BSIs) caused by Gram-negative bacteria (*Enterobacteriales*) with extended-spectrum beta-lactamase (ESBL)-type resistance gave a mortality rate of more than 70%, compared to 20% or less for malaria infections and BSI with susceptible bacteria (Blomberg 2005 & Blomberg 2007).

Antimicrobial resistance (AMR) threatens the very core of modern medicine and the sustainability of an effective, global public health response to the enduring threat from infectious diseases (WHO 2015). An increasing prevalence of ESBL-producing *Enterobacteriales* (ESBL-E) are among the most urgent global threats, and ESBL-E are by WHO ranked on priority one among pathogens in need of new treatment (WHO 2018). Fecal carriage of ESBL-E is a potential risk for transmission and infection. We have previously shown in a study from Tanzania (Fig. 1) that around 2/3 of infants below three months of age had fecal carriage of ESBL-E (Tellevik, 2016).

ProRIDE Trial in Tanzania

Probiotics are live microorganisms that, when administered in adequate amounts, confer a benefit to the host. Probiotics are currently widely used in newborns and children (Lenfestey 2017). They have proven beneficial effects in preterm infants with reductions in the incidence of necrotizing enterocolitis (NEC) and sepsis (AlFaleh 2014 & Rao 2016). For very preterm infants the use of probiotics in high-income countries has entered what has been called a “golden age”, and similar beneficial effects have also been observed among preterm infants in low- and middle-income countries (Deshpande 2017). It is important to acknowledge that

there are numerous probiotic products with possibly strain-specific effects (Lenfestey 2017).

In preterm infants, multiple-strain probiotics have proved more efficient in reducing NEC, sepsis and mortality than single-strain products (Chang 2017).

In a recent study from India, more than 4500 infants were randomized to receive either the probiotic bacteria *Lactobacillus plantarum* along with fructo-oligosaccharide, a plant-derived prebiotic (the combination of probiotic and prebiotic is coined “synbiotic”) or placebo (Panigrahi 2017). The synbiotic treatment was started on day 2-4 of life and was given for 7 days. This simple intervention reduced the composite outcome severe infections and/or death

[figure not shown]

Fig. 1. Prevalence of ESBL carriage in different age groups. The graph shows the prevalence (%) of ESBL carriage among the participants when categorized into five different age groups.

ProRIDE Trial in Tanzania

by 40%, from 9.0% in the placebo group to 5.4% in the synbiotic group (Fig. 2). This study has caused great attention in the scientific community and in the general public. Panigrahi has suggested that more studies are needed in order to develop guidelines for clinical care (The Wire 2017).

[figure not shown]

Fig. 2. Morbidity and mortality in infants given synbiotic versus placebo. Panigrahi, Nature 2017

A stable and resilient commensal gut microbiota is essential for “colonization resistance”; the ability to prevent intestinal colonization and invasion by pathogens. Resurrecting the gut microbiota by the use of probiotics has recently been put forward as a potential new strategy in combatting intestinal carriage of multi-drug-resistant (MDR) bacteria (Pamer 2016). To what extent probiotics directly reduce the spread of AMR is still much under investigation (Arthur 2016). However, probiotic bacteria can produce bacteriocins that improve mucosal integrity and thereby reduces the pathogenic bacterial population and promote “colonization resistance” (Pamer 2016), but there is so far no data on which probiotic strains that most effectively may reduce AMR in children. In adults and older children lactobacilli are often used to prevent or treat other conditions like antibiotic-associated diarrhea, gastroenteritis and infantile colic (Agamennone 2018 & Gutiérrez-Castrellón 2017). However, in breastfed infants, bifidobacteria constitute more than 80% of the gut microbiota (Fig. 3) and has several beneficial effects that make them attractive as probiotic agents for this age group.

ProRIDE Trial in Tanzania

In infants, *B. infantis* given in combination with human milk decreases the level of *Enterobacteriales* in the feces (Underwood 2015). In a clinical trial, we observed that among extremely preterm infants supplemented with a probiotic product containing bifidobacteria and lactobacilli, we found no ESBL-E in stool samples despite massive exposure to antibiotic therapy. In contrast, ESBL-E was detected in the stool of moderate preterm infants and full-term infants not given probiotics and

[figure not shown]

Fig. 3. Level of Bifidobacteria in the gut during different stages in life (by [name]).

with less or no antibiotic exposure (Esaiassen 2018). In this study (Esaiassen 2018), a metagenomics approach was used in order to analyze the gut microbiota and antibiotic resistome.

1.2 Main challenges and gaps of knowledge

Except from the study by Panigrahi (Panigrahi 2017) there is little data on the effect of probiotics in reducing mortality and infection-related morbidity in infants in low-income countries. There is also very limited clinical data on the effect of probiotics to reduce AMR carriage and AMR-related infections in infants and children, even though this approach has been put forward as a promising new strategy. Increasing AMR, according to the World Health Organization, is one of the most important threats to human health (www.who.int/entity/drugresistance/en). It affects both high- and low-income countries, but consequences are more severe in low income countries due to the prohibitive costs and thus

ProRIDE Trial in Tanzania

lack of specific diagnostic and second line antibiotics. No randomized clinical trial (RCT) has investigated whether probiotics may reduce ESBL-E carriage in infants.

1.3 Rationale to conduct this study

Our own research has shown a high mortality of Tanzanian children with ESBL-E infections (Blomberg 2005 & Blomberg 2007), a high carriage rate of ESBL-E in Tanzanian infants (Tellevik 2016) and promising results using probiotics to reduce AMR (Esaiassen 2018). The recent large RCT from India showed a reduction in severe infections and death among newborns given probiotics/synbiotics (Panigrahi 2017), and these beneficial findings are supported by data from systematic reviews indicating a reduction in sepsis and mortality in preterm infants given probiotics. However, studies in other developing countries are needed to confirm the positive findings from the Panigrahi trial.

We therefore propose to do an RCT on probiotics versus placebo in healthy Tanzanian infants. The primary endpoints, for which the study is powered, is a reduction in the composite outcome mortality and hospitalizations. Secondary endpoints are rates of ESBL-E gut carriage, growth, microbiota/metabolome composition and gut inflammatory markers.

1.4 Study hypothesis

Our hypothesis is that probiotics will significantly reduce the composite outcome death and/or infections in children up to 6 months of age. We hypothesize that this reduction will partly be mediated by a concomitant reduction in prevalence of ESBL-E-carriage in this group of children.

2. Objectives of the study

2.1 Overall objective of the study

The present clinical trial will evaluate whether 4 weeks administration of probiotics in the first 4 weeks of life can reduce mortality and/or hospitalizations, and colonization with ESBL-E, among infants in Haydom and surrounding area, Tanzania.

2.2 Specific objectives of the study

- 2.2.1** To assess and compare mortality among two groups of the study participants (i.e. probiotic and placebo group) in Haydom and surrounding area, Tanzania.
- 2.2.2** To determine and compare episodes of infections (i.e. sepsis, diarrhea, etc) leading to hospitalization among the two groups of study participants in Haydom and surrounding area, Tanzania
- 2.2.3** To determine and compare the prevalence of ESBL-E carriage between the two groups of study participants at six weeks and six months follow-up.
- 2.2.4** To determine and compare the bacterial causes of sepsis, including antimicrobial susceptibility patterns, in and between the two groups of study participants.
- 2.2.5** To assess and compare the effect of probiotics on growth between the two groups of study participants.
- 2.2.6** To determine and compare the gut microbiota composition and diversity between the two groups of study participants.
- 2.2.7** To determine the genetic characteristics of ESBL-E and other MDR isolates from carriage and clinical samples.
- 2.2.8** To determine the bacterial causes of sepsis, including antimicrobial susceptibility patterns for all children under 6 months of age admitted with fever during the study period.
- 2.2.9** To determine gut inflammatory markers from children at 6 month follow-ups

2.3 Study end point measures

2.3.1 Primary end point

- Prevalence of the composite outcome death and /or hospitalizations at six months of age.

2.3.2 Secondary end points

- Prevalence of ESBL-E carriage at six months of age.
- Rates of hospitalizations up to six months of age.
- Rates of confirmed sepsis episodes up to six months of age.
- Growth monitored by height and weight up to six months of age.
- Stool microbiota/metabolome composition including antibiotic resistome analysis (metagenome sequencing) at six weeks and six months of age.
- Genetic characteristics of ESBL-E and other MDR isolates from carriage and clinical samples.
- Characteristics of gut inflammatory markers

3.0 Methods

3.1 Study design

This will be a single-center randomized double-blinded controlled clinical trial (RCT) with two arms:

Arm 1: The active group will receive the investigational product (IP); a commercially available multi-strain probiotic product (LaBiNIC® probiotic drops, Biofloratech Ltd, Surrey, UK. Five drops (0.2 ml) contain 1.8×10^9 CFU *Lactobacillus acidophilus*, *Bifidobacterium infantis* and *Bifidobacterium bifidum* (equal amount of all three strains). The product is already widely used in the UK (at hospitals in the National Health Service) and in other European countries (Robertson 2020, Klingenberg 2019). The product also recently received the Pharmacy Grade Certificate A-Grade by the South African Pharmacy Council, valid until 31st of December 2021 (attached copy).

LaBiNIC® probiotic drops can be stored at room temperature, provided this does not exceed 25 °C for prolonged periods (a few hours at 30 °C causes no degradation). No refrigeration is needed for storage. The product is 100% dairy-, gluten-, egg-, soya- and allergen-free. It contains no animal products, no preservatives, no colouring products and/or no sweeteners. It is manufactured to GMP and GPP WHO standards. All batches are microbiologically tested for safety and composition.

Arm 2: The placebo group will receive placebo drops; a MCT-oil and AEROSIL® 200 Pharma (the latter is an additive for food and pharma products with a high quality standard, and with production processes based on quality concepts such as; ISO 9001, HACCP, FAMI-QS and IPEC-GMP). The MCT-oil and AEROSIL® 200 Pharma are also constituents of the active IP. The placebo is produced by the same company that manufacture the IP (Biofloratech Ltd, Surrey, UK). The MCT-oil is used as a vehicle for the probiotic bacteria in the IP, and the taste and colour is identical, and it will be produced in identical bottles to the IP.

ProRIDE Trial in Tanzania

The drops for both arms will be dispensed in identical bottles. All infants will be given 5 drops daily from inclusion and for a period of four weeks (“to bottle empty”). Previous studies in developing countries have used from 7 days (Panigrahi 2017 - India) to 60 days (Pernicia 2017 - Botswana) intervention with probiotic supplementation in infants.

3.2 Study site

This will be a single-centre study to be conducted at Haydom Lutheran Hospital (HLH) and surrounding area. HLH is located in the Mbulu district, at the western end of Manyara region in the North-Central Tanzania, about 300 km south-west from Arusha. The HLH catchment area consists of 4 administrative divisions, 3 districts and 2 regions. These are the Dongobesh and Haydom divisions in Mbulu District, the Basotu Division in Hanang District (Manyara Region), and the Nduguti Division in Mkalama District (Singida Region). The hospital serves more than 2 million population from five regions. HLH has strong and well-established research infrastructure, and over ten years has been involved in community research, which has built trust between the hospital and community around (Mduma, 2014). There are annualy more than 3900 deliveries and the neonatal mortality rate is around of 43/1000 live births.

The hospital has a track record of conducting clinical trials, including the Early Life Intervention in Childhood growth and development (ELICIT), the Effectiveness of Quadruple Fortified Salt in Improving Hemoglobin Levels among Anemic Women of Reproductive Age (18-49 Years) in Rural Low Resource Setting (Salt study trial) and clinical trials on neonatal resuscitation evaluating the Helping Babies Breathe program. HLH has laboratory capacity with required equipment's and trained staff to do clinical trials.

3.3 Study setting and population

Newborn infants delivered at HLH or outside hospital will be eligible for inclusion.

ProRIDE Trial in Tanzania

Mothers to potential eligible participants (newborn infants) will be approached and informed about the ProRIDE-study at home or when attending their last antenatal clinic visits before delivery. Those mothers who give written consent for potential participation of their future child will be recruited to participate in the study, and after giving birth the newborn will be screened for eligibility before being randomized in the study. We intend to include a total of 2000 newborn infants to participate in the study, half of these i.e. 1000 will receive a multi-strain probiotic product and the other 1000 will receive placebo.

3.4 Research question and statistical power

The research question is: Among term born healthy infants in Tanzania (P-population), will treatment with probiotics (I-intervention) compared to placebo (C-comparison) lead to a 40% reduction in hospitalizations and death, and in fecal carriage of ESBL-producing bacteria (O-outcome)?

Infant mortality rate in Tanzania was in 2017 reported at 4.4%. We do not have exact data for the Mbulu district, but we assume a similar rate. Serious infections leading to hospitalization are probably equally common, but hospitalization rates may depend on available access. In the Panigrahi study, the synbiotic product was given for only 7 days, and it reduced the composite outcome death and/or infection from 9.0% to 5.4% during the first 2 months of life. In our study, the intervention will continue for around 4 weeks and follow-up will continue until 6 months of life. We consider a similar reduction in the composite outcome death and infections leading to hospitalizations from 9.0% to 5.4%, as in the Panigrahi study, to be clinically relevant. To find this difference with a study power of 85% at 5% significance level we will need a sample size of minimum 924 cases in each arm; thus 1848 infants. In order to allow for drop-out we aim to include 1000 infants in each arm. We believe it is realistic to include this number of infants within a 12-month recruitment period.

ProRIDE Trial in Tanzania

With this number of infants, we will also have sufficient power to detect a minimum of 30% reduction in ESBL-carriage rate (from around 50% to 35%) at six months of age.

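### Does the 85% power belong to a different outcome from the primary endpoint?

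*Protocol*

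**What the plan says.** **Power.** Protocol 3.4 asks whether probiotics will "lead to a 40% reduction in hospitalizations and death", with no mention of infection. It then cites a synbiotic trial from India, saying "it reduced the composite outcome death and/or infection from 9.0% to 5.4% during the first 2 months of life", and notes that follow-up here runs to six months. The difference it sizes for is "a similar reduction in the composite outcome death and infections leading to hospitalizations from 9.0% to 5.4" per cent. That gives at least 924 per arm for 85% power at the 5% level, raised to 1000 per arm for drop-out. SAP 11 repeats this.

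**Local rates.** Protocol 3.4 puts infant mortality at 4.4%; SAP 11 puts it at about 4%. On admissions, the protocol says "Serious infections leading to hospitalization are probably equally common, but hospitalization rates may depend on available access".

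**Endpoint.** Protocol 2.3.1 defines it as "Prevalence of the composite outcome death and /or hospitalizations at six months of age". SAP 26 has the same definition, and SAP 8, 9 and 12 also set no infection limit. Protocol 1.3 says: "The primary endpoints, for which the study is powered, is a reduction in the composite outcome mortality and hospitalizations".

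**Other wordings.** The hypothesis in Protocol 1.4 is that "probiotics will significantly reduce the composite outcome death and/or infections in children up to 6 months of age". Objective 2.2.2 compares "episodes of infections (i.e. sepsis, diarrhea, etc) leading to hospitalization". The Summary says the trial is powered for a 50% reduction in infection-related illness and death.

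**The concern.** The sentence that carries the power names a narrower outcome than the one to be tested. An infant admitted for a reason other than infection counts towards the endpoint but not towards the outcome in the power sentence. The 9.0% and 5.4% also come from another trial's death-or-infection composite over two months, whereas this trial counts any admission over six. No six-month placebo rate is stated for death or any hospitalization.

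If many admissions have causes that the product cannot influence, they add events equally to both arms, dilute the relative effect and lower the power. A reader of a null result might then take 85% power for a 40% reduction as established for the tested endpoint when it was only assumed. The Summary's 50% adds doubt about which effect the trial was built to find.

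**Working it through.** **Inputs.** Rates of 9.0% and 5.4%, 85% power, 5% level, 924 and 1000 per arm (Protocol 3.4); two-sided test (SAP 17); 1:1 allocation (SAP 10).

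**1. Reproduce 924.** Pooled two-proportion formula without continuity correction:

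n = [1.960·√(2·p̄·(1−p̄)) + 1.036·√(p₁(1−p₁) + p₂(1−p₂))]² / (p₁−p₂)²

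With p₁ = 0.090, p₂ = 0.054 and p̄ = 0.072:
- √(2 × 0.072 × 0.928) = 0.3656
- √(0.0819 + 0.0511) = 0.3647
- numerator (0.7165 + 0.3780)² = 1.198
- denominator 0.036² = 0.001296
- n = 924.2 per arm

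Power is 85.0% at 924 per arm and 87.6% at 1000. The effect is (9.0 − 5.4)/9.0 = 40%.

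**2. The Summary's 50%.** For 9.0% versus 4.5%, the same formula gives 556.6 per arm. Power is 97.1% at 924 and 98.0% at 1000. A trial sized for 40% more than covers 50%.

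**3. The local figures.** The documents never add deaths and admissions, so these sums are only a plausibility check. Protocol: 4.4% + 4.4% = 8.8%. SAP: 4% + 4% = 8%. With a 40% reduction:

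| Placebo rate | Power, 924 per arm | Power, 1000 per arm |
|---|---|---|
| 8.8% | 84.1% | 86.9% |
| 8.0% | 80.3% | 83.3% |

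The sums are crude in both directions. They use an infant mortality rate from the general population for a six-month endpoint in healthy newborns of at least 2.0 kg, and they ignore overlap between deaths and admissions. Those features push them too high. They also leave out admissions not due to infection, which pushes them too low.

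**4. Which way could an error go?** The rates below are illustrative assumptions with no source in the documents. The base case is 85.0% at 924 and 87.6% at 1000.

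| Assumption | Power, 924 per arm | Power, 1000 per arm |
|---|---|---|
| 40% reduction, placebo 6% | 67.5% | 70.9% |
| 40% reduction, placebo 10% | 88.7% | 91.0% |
| 40% reduction, placebo 12% | 93.9% | 95.4% |
| 9.0% vs 5.4%, plus 1 point in both arms | 80.6% | 83.6% |
| 9.0% vs 5.4%, plus 3 points in both arms | 72.5% | 75.8% |
| 9.0% vs 5.4%, plus 5 points in both arms | 65.7% | 69.2% |

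A broader endpoint raises power if the 40% reduction applies to all of it, and lowers power if the added admissions are unaffected. The documents do not settle which applies.

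**5. Would an analyst be unsure what to count?** No. Protocol 2.3.1 and SAP 26 define the endpoint in the same terms, and SAP 8, 9 and 12 agree. Objective 2.2.2 is a separate objective on infection episodes, next to 2.2.1 on mortality, and does not define the composite. The loose wording in Protocol 1.4 is a hypothesis, not an endpoint definition.

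**The case for a change.** The strongest case for a change is that Protocol 1.3 claims power for the primary endpoint while Protocol 3.4 and SAP 11 calculate it for something narrower and borrow rates from a shorter window. Dilution by unaffected admissions is a real mechanism: with all 1000 per arm analysed, about 0.6 added points in both arms already bring power down to 85%. If the 40% reduction holds on the whole endpoint, 85% at 1000 per arm needs a placebo rate of at least about 8.4%, and the SAP's figures simply added fall short of that. A caveat would cost only words.

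The mismatch itself stands, as does the absence of a stated six-month rate for the unrestricted endpoint. The inference from these to a faulty power claim does not. Section 3.4 discloses the two-month source and the six-month follow-up, adopts 9.0% to 5.4% as a clinically relevant difference, and gives the power to find that difference. This is a conditional statement, as every power statement is. The same section words its research question on unrestricted hospitalization and death. The sizes of the assumed dilution come from outside the documents, so a table built on them would not improve the plan. A reader weighing a null result has the odds ratio and 95% confidence interval promised in SAP 16, which show directly what effects remain plausible.

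**Conclusion.** The concern does not call for a change. Two clerical inconsistencies remain: the power sentences limit hospitalization to infection where the endpoint does not, and the Summary says 50% where the calculation uses 40%. Neither alters what is counted, how it is tested, the type I error, the estimate or its interval. SAP 11 reports recruitment of all 2000 infants as finished, so the sample size cannot be revisited.

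The stated 85% is correct for 924 analysed per arm, and 87.6% for 1000, on the assumption that 9.0% versus 5.4% applies to death or any hospitalization at six months. The protocol's own local figures, simply added, give 84% and 87%; the SAP's give 80% and 83%. True power could be higher or lower, and the documents do not show the stated figure to be wrong. Aligning the wording would be an editorial tidy with no gain for the analysis.
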